The study is observational, retrospective-prospective, multicenter "real-life" study involving 26 centers belonging to the SEIFEM group. Regarding the retrospective part, clinical data will be collected on all patients with LMA FLT3+ (ITD or TKD mutation) treated with Gilteritinib from when the drug was approved and marketed in Italy (April 2, 2020) until April 30, 2022. Enrollment in the prospective cohort will have an estimated duration of 24 months from the time of study approval. Patients enrolled in the last month will be followed for six months from the date of enrollment to check for the occurrence of any infections. For each case of a patient receiving salvage monotherapy with Gilteritinib, a control patient with LMA R/R FLT3+ on salvage chemotherapy should also be included.

Study Duration.

Relative to the prospective part, the study will have a total duration of 24 months from the first patient enrolled and six months of observation from the last patient enrolled.

Population

Inclusion criteria:

- All patients with FLT3+ relapsed/refractory AML to any line of therapy treated with Gilteritinib
- Patients ≥ 18 years of age
- Signature of appropriate informed consent

Exclusion criteria:

- Patients < 18 years old

Study Objectives.

The purpose of the present retrospective/prospective study is to evaluate the "real life" incidence of infectious complications in patients with relapsed/refractory FLT3+ AML treated with Gilteritinib.

Primary objective

To assess "real-life" in patients with relapsed/refractory FLT3+ LMA treated with Gilteritinib the absolute infectious risk and compare it with relapsed/refractory patients receiving chemotherapy.

Secondary objectives.

- To assess the site, incidence and outcome of bacterial/fungal/viral infections in this patient setting
- To assess the need for hospitalization and the duration of hospitalization
- To analyze the different antifungal prophylaxis policies in different Hematology Centers and correlate them with the incidence of infection
- To analyze the incidence of side effects related to the use, in combination with Gilteritinib, of antifungal/antibacterial/antiviral drugs (in prophylaxis/therapy).

Methods

The proposed study is retrospective-prospective, multicenter, observational.

Data will be retrospectively collected from all cases observed from April 2, 2020 until April 30, 2022 about the infectious event and related treatment information (database attached).

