In the prospective cohort, enrollment will have an estimated duration of 24 months from the time of study approval. Patients enrolled in the last month will be followed for six months thereafter to check for the occurrence of any infections.

Data from patients with gilteritinib monotherapy and data from patients for whom the clinician's choice is the use of chemotherapy (consisting, for example, of the following regimens: FLA-IDA, MICE, MEC, intermediate/high-dose cytarabine) will have to be analyzed to assess the infectious risk associated with gilteritinib monotherapy.

It is reiterated that since this is an observational study, the choice of therapy is at the discretion of the treating hematologist and independent of enrollment in this study.

Informed consent will be sought from all patients still alive at the time of initiation of data collection and from patients whose data will be collected prospectively. However, it should be noted that since this is a study that mainly considers patients with relapsing hemopathies that could be complicated by life-threatening infections, the rate of obtainable consents may be reduced due to the mortality of these hemopathies.

The incidence of infection will be related to the following variables:

- Age
- Sex
- Comorbidities
- Type of antimicrobial prophylaxis performed
- Type of FLT3 mutation (ITD vs TKD)
- Type of response to treatment
- Hospitalization and duration

Any side effects related to the combination of Gilteritinib with antimicrobial drugs used in prophylaxis/therapy by different centers will also be evaluated.

The study will not affect normal care practice in any way, as there is no blood sampling for patients. Each patient and each control will be assigned an identification code that will allow the omission of any reference that would allow patient recognition.

Clinical information will pertain to the coordinating center and will be collected within a database.

Based on the following considerations:

- it is assumed that the reference population, or target population from which the sample is drawn (78 patients), is Gaussian distributed with unknown variance;
- the null hypothesis (superposibility of the two populations: sample and target) is rejected if the sample mean differs from the mean value of the reference population by an amount, in absolute value, equal to or greater than 36.7 percent of the standard deviation;

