- we adopt, for testing the hypotheses (null and alternative), the two-tailed Gauss z-test with $\alpha = 0.05$ (error of the first kind) and $\beta = 0.10$ (error of the second kind), which implies, as is well known, a test power of 90%;

at least 78 patients are expected to be enrolled.

The analysis will be aimed at evaluating the distribution of infectious events (viral/bacterial/fungal) and identifying parameters that significantly influence the outcome of infectious complication.

With regard to descriptive statistical analyses, central tendency, variability, symmetry and kurtosis will be calculated, all accompanied by appropriate graphical representations; with regard to inferential analyses, in addition to multivariate binary logistic regression, parametric and nonparametric hypothesis testing will be carried out, respectively, for quantitative variables with parametric tests such as: Student's t-test, Fisher's F-test, etc. and for categorical variables by nonparametric tests such as: chi-square, Mann Whitney's U, Fisher's exact test, etc. Only results with p-values ≤ 0.05 will be considered statistically significant.

The study does not involve any expenses related to data collection or additional examinations.

Italian Hematology Centers belonging to the SEIFEM Group, which includes both university and hospital facilities, will participate in the study (Appendix 1: list of participating centers).

Data collection and analysis and report preparation will be the responsibility of the scientific board.

Dissemination of results

Publication of results in leading international scientific journals dealing with topics related to hematology and infectious diseases. Also, presentation of results at major national and international hematology congresses, (American Society of Hematology, European Hematology Association, Italian Society of Hematology)

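### The logistic model has no limit on its size: with all listed variables in one ordinary maximum-likelihood fit, 78 patients give at most about 4 events per coefficient and inflate the odds ratios

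*Combined protocol and SAP*

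**What the plan says.** The statistical paragraph at the end of Methods states that "in addition to multivariate binary logistic regression, parametric and nonparametric hypothesis testing will be carried out". The other methods it names are two-group or contingency-table tests, so logistic regression is the only multivariable method in the plan. Earlier in Methods, a list opens with "The incidence of infection will be related to the following variables". It has seven items: age, sex, comorbidity, antimicrobial prophylaxis, ITD or TKD mutation, treatment response, and hospital stay with its length. The primary objective adds a comparison of gilteritinib with chemotherapy.

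On size, Methods says "at least 78 patients are expected to be enrolled". That number comes from a one-sample z-test on a mean, with a difference "equal to or greater than 36.7 percent of the standard deviation". Study design adds that for each gilteritinib case "a control patient with LMA R/R FLT3+ on salvage chemotherapy should also be included". The plan does not say whether the 78 includes these controls.

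The plan does not state which variables enter the model, how they are chosen, how the model is estimated, or how many infections are expected.

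**The concern.** Maximum-likelihood logistic regression is biased away from the null when there are few events per coefficient. At very low ratios some data sets also separate, so that an odds ratio has no finite estimate. The sample size was not set for this model, and nothing in the plan prevents every listed variable from entering it.

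The treating hematologist chooses the therapy, so the unadjusted tests do not deal with confounding. Any adjusted odds ratio for gilteritinib, and any joint analysis of prophylaxis and other factors, would have to come from this model. Only results with p at or below 0.05 will count as significant, and selection on that threshold favours exaggerated estimates further.

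**Working it through.** **1. The plan's own figure.** One-sample two-sided z-test, alpha 0.05, power 90%, difference 0.367 SD:
n = ((1.960 + 1.282) / 0.367)² = 78.01. The plan's 78 reproduces. No logistic model enters this calculation.

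**2. Number of coefficients (assumed).** Seven items, with hospitalization and its duration as two terms, make 8. Treatment group makes 9. Eleven would need two extra factor levels, for example in prophylaxis and response.

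**3. Upper limit on events per coefficient.** The information in a binary outcome is limited by the smaller outcome group, which is at most half of N whatever the infection rate.
- N = 78: 39/9 = 4.3; 39/11 = 3.5.
- N = 156 (78 cases plus 78 controls): 78/9 = 8.7; 78/11 = 7.1.

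**4. Illustrative event counts.** The documents give no rate for any infection. Two background rates serve as markers: 25% (invasive fungal infection) and 45.9% (grade 3 or higher febrile neutropenia).
- N = 78: 0.25 × 78 = 19.5 and 0.459 × 78 = 35.8 events. Per coefficient: 2.2 and 4.0 with 9 terms, 1.8 and 3.3 with 11.
- N = 156: 39.0 and 71.6 events. Per coefficient: 4.3 and 8.0 with 9 terms, 3.5 and 6.5 with 11.

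**5. Simulated bias.** Relative bias = mean estimated log odds ratio / true log odds ratio − 1. Covariates were independent (for 7 and 11 coefficients, two continuous and the rest binary with prevalence 20-60%). There were 1000 to 6000 replicates per setting, and separated data sets were left out of the maximum-likelihood mean.

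| N | Coefficients | True effects | ML bias at 25% events | ML bias at 45.9% events |
|---|---|---|---|---|
| 78 | 11 | one OR of 2 | +27% | +20% |
| 78 | 11 | all ORs 1.5 | +32% | +21% |
| 78 | 11 | all ORs 2 | +41% | +30% |
| 78 | 9 | one OR of 2 | +20% | +17% |
| 78 | 7 | one OR of 2 | +17% | +10% |
| 156 | 11 | one OR of 2 | +9% | +11% |
| 156 | 11 | all ORs 2 | +19% | +11% |
| 156 | 9 | one OR of 2 | +8% | +7% |

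Separate runs with 9 to 11 coefficients and one true OR of 2 gave +16% to +28% at N = 78 and +4% to +10% at N = 156. With 11 coefficients and 25% events at N = 78, 3-10% of data sets separated.

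On the odds ratio scale, a true OR of 2 inflated by 15% becomes 2^1.15 = 2.2, and by 30% becomes 2^1.30 = 2.5.

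**6. Firth penalisation.** Bias stayed between −5% and +5% across all the runs. The SD of the log odds ratio also fell (N = 78, 11 coefficients): from 0.76 to 0.59 at about 21 events, and from 0.68 to 0.55 at about 36.

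**7. A shorter model alone.** With four covariates, ML bias was 6-10% at N = 78 and 3-6% at N = 156.

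**The case against.** The strongest reply is that the plan never commits to the model criticised here. It says that infection will be related to seven items, which the named univariable tests could do. It does not say that all of them enter one regression, and it names no estimator. Part of this stands: the point is conditional, and maximum likelihood is only the usual default. But the plan sets no limit either, so the oversized model is permitted.

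Secondly, 78 may not be the size of the comparative analysis. The inclusion criteria admit patients treated with gilteritinib, the calculation is one-sample, and controls are added case by case. A model with a treatment term could therefore have about 156 patients, and 78 is in any case a minimum. This stands, and it is why the smaller range is given beside the larger one. On that reading, a risk-factor model in gilteritinib patients alone would still have about 78 patients and 8 terms, or at most 39/8 = 4.9 events per coefficient.

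Thirdly, imprecision outweighs bias: 19% of ln 2 is 0.13, against an SD of 0.76. This is true, but Firth reduces the SD as well. Fourthly, shortening the covariate list removes much of the bias without penalisation. That is also true (step 7). Penalisation lowered both bias and SD in the four-covariate model too.

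A reader might infer more than the documents support:
- That the plan specifies 11 coefficients on 20-36 events with a 20% bias. The 11 needs assumed factor levels, both rates come from gilteritinib patients and neither is for any infection, and 20% is one value in a wide range.
- That separate full models for each infection type are planned. They are not stated.
- That these odds ratios are the main inferential output. The primary objective is absolute infectious risk and its comparison with chemotherapy.

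**Conclusion.** The concern holds in conditional form. If all listed variables enter one ordinary maximum-likelihood model, 78 patients give at most about 4 events per coefficient with 9 terms. Log odds ratios are then inflated by roughly 15-30% when one true OR is 2, and by up to about 40% under other assumed effects. With about 156 patients the inflation is roughly 4-19%.

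These sizes rest on an assumed 9 to 11 coefficients, borrowed event rates, an assumed analysis N, and independent simulated covariates; correlated covariates or sparse categories could change them. The limit of 39 does not depend on the event rate. Interval coverage was not examined.

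This is more than missing detail, because the default fit of the named model is worse than an available alternative in both bias and SD in every setting tested. It does not invalidate the study. The change should be made before analysis.

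**What to change.** In the statistical part of Methods:

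- State that the logistic model is fitted with Firth penalisation and reported with profile-likelihood intervals.
- Fix a short covariate list in advance: treatment group, age, one comorbidity summary, and prophylaxis at start. As four single coefficients this allows at most 39/4 = 9.75 events per coefficient at N = 78; extra prophylaxis categories would lower it.
- Report the other listed variables descriptively. Response and hospital stay are known only after treatment has begun, which is a further reason to keep them out of a baseline adjustment.
- Do not fit a separate full model for each of bacterial, fungal and viral infection, where events will usually be fewer.
- State the analysis N, whether the 78 includes controls, and the expected number of infections.

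The cost is analysis wording only: no new data are needed, and standard software suffices. The downside is slight shrinkage of the estimates and fewer variables examined jointly.

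### The seven-factor infection screen and the secondary analyses share one unadjusted p ≤ 0.05 rule, with no multiplicity control and no exploratory label

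*Combined protocol and SAP*

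**What the plan says.** The statistical paragraph at the end of Methods in the combined protocol and SAP gives one criterion, without distinguishing between analyses: "Only results with p-values ≤ 0.05 will be considered statistically significant". It states the purpose of the analysis partly as "identifying parameters that significantly influence the outcome of infectious complication". The methods are multivariable logistic regression plus a set of parametric and nonparametric tests that is left open-ended.

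Earlier in Methods, "The incidence of infection will be related to the following variables" introduces seven items: age, sex, comorbidities, antimicrobial prophylaxis, FLT3 mutation type, treatment response, and hospitalization with its duration.

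Study Objectives names one primary objective, the infectious risk on gilteritinib compared with chemotherapy. The secondary objectives cover the site, incidence and outcome of infections by type, hospitalization, centre prophylaxis policies in relation to infection, and side effects of antimicrobials combined with gilteritinib.

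The documents contain no multiplicity adjustment, no order of testing, no count of tests and no statement that any analysis is exploratory. Error rates appear only in the sample-size text, and there for a single hypothesis.

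**The concern.** A 5% threshold limits false positives to 5% for one test. Here it is applied to a search through several candidate factors, and the stated product of that search is a set of significant ones. Followed as written, the plan lets a chance association with, say, prophylaxis type or mutation type be published as a significant determinant of infection, with nothing to tell the reader that it came from a screen. The protocol's background says that real-life experience with infections on gilteritinib is lacking, so such a claim could carry weight.

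Leaving p-values unadjusted is acceptable in an observational study if the analyses are presented as exploratory. This plan does not present them that way.

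**Working it through.** **1. What the stated alpha covers.** Inputs from Methods: two-sided alpha 0.05, power 90%, and a difference "equal to or greater than 36.7 percent of the standard deviation". The one-sample z-test formula gives

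n = ((1.960 + 1.282) / 0.367)² = 78.01,

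which agrees with "at least 78 patients are expected to be enrolled". Power at n = 78 is 90.0%. The only error-rate calculation in the plan therefore concerns one test of one hypothesis. It allows nothing for the factor screen.

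**2. The screen as listed.** Inputs: seven variables and a threshold of 0.05 per test. Assumptions: one test per variable, independent tests, all null hypotheses true.

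- Chance of at least one false positive: 1 − 0.95^7 = 0.302.
- Expected false positives: 7 × 0.05 = 0.35.

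**3. A wider set of tests (assumed).** The plan does not say that each variable is tested against each infection type. If it were:

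| Assumed family | Tests | At least one false positive, independent | Expected number |
|---|---|---|---|
| 7 variables × any infection | 7 | 30.2% | 0.35 |
| 7 × 3 infection types | 21 | 65.9% | 1.05 |
| 7 × (3 types + any infection) | 28 | 76.2% | 1.40 |

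About 14 independent true-null tests are needed before the chance passes one half (1 − 0.95^14 = 0.512).

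**4. Correlation.** For the 21-test family, z-tests were simulated with 200,000 replicates:

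- Correlation between infection types of 0.3, 0.5, 0.7 and 0.9 gives 64%, 61%, 55% and 46%.
- Correlation of 0.3 or 0.5 among both variables and types gives 59% or 49%.

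Correlation leaves the expected number unchanged.

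**5. Two things that lower both the chance and the expected number.**

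- *True associations.* A factor that really is related to infection cannot produce a false positive. If three of the seven were real, four nulls would remain: 1 − 0.95^4 = 0.185, with 4 × 0.05 = 0.20 expected.
- *Conservative tests.* Fisher's exact test is among those named. For a two-level factor in 78 patients, with assumed event rates of 5% to 50%, its true size at nominal 0.05 is about 0.004 to 0.031 for a 39/39 split and 0.020 to 0.036 for a 58/20 split. If all seven tests had size 0.03, the chance would be 1 − 0.97^7 = 0.192. Chi-square tests and logistic regression, also named, would not share this fully.

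**The case against.** The strongest reply is that this is an observational study with one labelled primary objective, that it claims nothing confirmatory for the secondary objectives, and that the alarming figures rest on a grid of tests the plan never sets out. Much of this stands.

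- The seven variables are tied to infection incidence only. The split by type appears in the statistical paragraph under "evaluating the distribution of infectious events (viral/bacterial/fungal", which can be read as descriptive. The 21- and 28-test families are therefore assumptions. A reader might infer that at least one false finding is more likely than not, but the one list in the plan gives 30%, which does not support that.
- A reader might also infer that the primary result is compromised by being one of many. It is not. A single primary comparison tested at 0.05 keeps its 5% error rate however many secondary tests are run. Whether its endpoint and test are adequately defined is a separate question.
- Read literally, the rule makes p ≤ 0.05 a necessary condition for significance, and does not say that every such result must be claimed. In ordinary use it works both ways, and the plan offers no further condition.

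The observational design does not answer the remaining point. The plan applies the word significant to every result below the threshold and makes the search for such factors an aim. Nor is seven clearly an overcount: hospitalization and its duration are two quantities, and comorbidities and prophylaxis type may each need more than one contrast.

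**Conclusion.** The concern holds for the predictor, infection-type, prophylaxis and outcome analyses. On the listed seven variables, the chance of at least one false significant factor is about 30%, six times the nominal 5%, assuming one independent test per variable and no true associations. True associations or exact tests would bring it lower. The figures of 66% and 76% are upper values under families of tests that the documents do not specify. Plausible correlation brings the 21-test figure to roughly 46–64%.

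The documents do not support the stronger conclusions that a false finding is probable or that the primary gilteritinib-versus-chemotherapy comparison is inflated. The defect affects how secondary findings may be described, not whether the study can be carried out. It should be corrected because the correction is simple and the current rule permits claims that the analysis cannot sustain.

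**What to change.** In the statistical paragraph of Methods:

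1. Confine the p ≤ 0.05 significance rule to the primary comparison of infection risk between gilteritinib and chemotherapy.
2. State that all other analyses are exploratory and will be reported as estimates with 95% confidence intervals.
3. For the seven-variable screen, write out the tests that make up the family, give p-values adjusted across it, and do not call unadjusted results significant. Benjamini-Hochberg or Holm would serve, and the choice matters less than fixing it in advance.

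This takes a few sentences and no additional patients or data. The downside is that fewer findings can be called significant. Under Holm with seven tests, for example, the smallest p-value must be at or below 0.05 / 7 = 0.0071.
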